#### **9.1.1.5 Assess Potential for Unmeasured Confounding**

Unmeasured confounding is a serious threat to the estimation of vaccine effectiveness using observational data [3-9]. There may be situations where the initial recommendations for vaccination, the vaccine distribution strategy, and the uptake of the vaccine may heavily influence the magnitude and direction of confounding. Since unmeasured and unknown confusion may be present we will perform the following strategies in order to minimise then:

- unvaccinated comparator will be matched by time zero of the vaccinated pair, birth year cohort (year; it will be broad till 2-years if not enough patients to select), sex, region of the primary care practice. If available information, patients living at nursing home will be matched). Several other confounder will be controlled for through adjustment in the Cox model.
- Since multiple COVID-19 vaccines are available, recipients of different COVID-19 vaccines will be also compared with the same unvaccinated comparator and among them in a head-to-head fashion. This choice would greatly diminish, if not eliminate, confounding by indication.

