### 9.3.1 Exposure Assessment and Time At Risk

Data will be collected from BIFAP database with data from Spain (described in [Data Sources](#)).

**Inclusion criteria** to the Source population: up-to-standard,  $\geq 1$  year baseline information in January 2021 in BIFAP. The last date of filling all the inclusion criteria will be the inclusion date. No restriction to age or sex will be applied.

**Exclusion criteria:** Patients with prevalent COVID vaccinations or infections ever before (i.e. washout period) the inclusion criteria will be excluded.

**Stop date:** the last moment of the following criteria will define the stop date to contribution: covid-19 infection, death, loss to follow-up and end of study period (the last date available in the data source at data collection).

**Exposure assessment:** The 1st vaccination recorded after the inclusion date will be the time zero for patients included in the vaccinated group, as explained in section 'Definition of Time Zero' [9.1.1.4](#).

From the source population, 10 individuals unvaccinated on or before time zero of the vaccinated pair (10:1) will be randomly selected among those with similar birth cohort, sex and region (matched criteria). Patients included in the comparison group, may be vaccinated later during their follow-up period and then contribute to the vaccinated group (from the date of vaccine administration ahead; i.e. time zero for the vaccinated group).

\*Note: All individuals vaccinated during their follow-up contribution will be included in the vaccinated group. While, a random selection of the unvaccinated individuals will be included as unvaccinated group.

The date and type of vaccine administered will be collected from the **Table of Vaccine** from BIFAP data model. In particular, Covid-19 vaccinations will be ascertained from official covid-19 vaccination registries and provided by the regional governments. The coding system is not known yet. The feasibility analysis will include an evaluation of the coding type, whether or not vaccines are recorded according to standardised system or not. We expect that either ATC07 (J07????) or National Code (CNF [Código Nacional de

Farmacia]) specific for pharmaceuticals in Spain is available for all vaccines administered.

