### **9.3.4 Covariate Assessment**

In order to control for measurable confounders in the analysis, the following variables will be collected: lifestyle characteristics (BMI, smoking alcohol use), comorbidities, comedICATIONS, and health care utilisation prior to or at time zero and updated every 21 days and at every change in the exposure period (i.e. when receiving D1, D2) at the patient level. Given that risk factors for COVID-19 infection are not currently well understood [30], we will measure covariates that are classically controlled for in pharmacoepidemiologic research and leaves room for the inclusion of risk factors yet to be determined.

As explained in [Data source](#), clinical events will be collected by using the International Classification of Primary Care (ICPC) and the International Classification of Diseases 9th Revision (ICD-9) medical terms (6,7).

The following variables will all be assessed as last status before time zero:

- Smoking status
- Body mass index
- Alcohol use

The following comorbidities (and others that may be shown to be associated with COVID-19 prognosis) will be assessed ever before time zero and updated:

- Diabetes mellitus (types 1 and 2)
- Hypertension record
- Cardiovascular disease
- Cerebrovascular disease
- Chronic respiratory disease
- Chronic kidney disease
- Chronic liver disease
- Cancer

- Immunodeficiencies including Human immunodeficiency virus and other immunosuppressing conditions
- Autoimmune disorders

Comedication use will be assessed through pharmacy dispensing and primary care physician prescribing records by ATC. Considered comedications may be indicative of comorbidities placing patients at higher risk or markers of health care-seeking behaviour and utilisation and may serve as markers of patients' history of other infections or be risk factors for severe COVID-19 disease themselves. The following comedications will be assessed during the year before time zero and updated:

- Antibiotics
- Antiviral medications
- Corticosteroids
- Non-steroidal anti-inflammatory drugs
- Other Analgesic
- Psychotropics
- Statins
- Immunosuppressant medication use

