## 9.4 Data Source

Data on patients will be obtained from primary care outpatient anonymised clinical records, dispensation in pharmacies of primary care prescriptions and diagnosis at hospital discharge from the Spanish public National Health System (SNS). Those data banks are unified in the data source so-called "Base de datos para la investigación Farmacoepidemiológica en Atención Primaria" (BIFAP) (8,9).

BIFAP includes information about patients' age, sex, life-style factors (i.e. body mass index (BMI), smoking status, alcohol consumption), clinical events (recorded by using

the International Classification of Primary Care (ICPC) and the International Classification of Diseases 9th Revision (ICD-9) medical terms (6,7)), anonymised primary care physicians' (PCPs) free-text notes, specialist referrals and discharge letters, prescriptions issued in primary care and their dispensations in pharmacies, vaccinations, laboratory test results and diagnosis at hospital discharge (recorded through the RAE-CMBD system) of around 13.7 million patients attended in a public primary care setting (7.4 of them aged  $\geq 18$  years). BIFAP covers 7 out of 19 districts in Spain and 57% of their population overall (as described in the Spanish Statistical Office (10)). In addition, currently, data on covid-19 infections resulting in an admission or discharge diagnosis to hospital (inpatient record) or intensive care unit as the setting of care are being incorporating to BIFAP. Figure 2:

BIFAP is fully funded by the Spanish Agency on Medicines and Medical Devices (AEMPS), belonging to the public Department of Health, and is maintained with the collaboration of the participant regions (8).

The records on the results of the COVID-19 laboratory test will be linked with BIFAP primary care profiles. Also, all vaccinations administrated against COVID-19 recorded in any setting will be linked with the primary care history in regions providing data. Particularly, vaccinations will be entered in the BIFAP's Table of Vaccines that in 2019 included around 61 million of recorded vaccinations.

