## 9.5 Study Size

All patients meeting the eligibility criteria in BIFAP will be included as source population. BIFAP includes information of around 7.7 million patients aged  $\geq 18$  years (as last updated version in 2018), which distribution by sex and age is as follows:

	TOTAL	18 - 19	20 - 24	25 - 29	30 - 34	35 - 39	40 - 44	45-49	50 - 54	55-59	60-64	65-69	70-74	75-79	80-84	85-89	90-110
TOTAL	7720843	252143	424740	465933	526002	647688	747020	717918	702323	658868	569616	493770	454787	350359	317844	246643	145189
Women	3991612	122805	209807	232836	265565	324008	369475	357547	352106	330858	290309	255848	242742	194252	187908	154500	101046
Men	3729231	129338	214933	233097	260437	323680	377545	360371	350217	328010	279307	237922	212045	156107	129936	92143	44143

Taking into account the estimated COVID vaccine effectiveness reported in clinical trials [75-78], varying assumptions of vaccine unexposed to exposed ratio, anticipated global sample sizes of patients aged  $\geq 18$  years in BIFAP, a cumulative positive symptomatic COVID cases of 60,57 per 100,000 people in 14-days in Spain (as reported on 22 March 2021 [when started the vaccination for general people, i.e. apart from health workers and nursing home residents] in [www.cnecovid.isciii.es/covid19/](http://www.cnecovid.isciii.es/covid19/)), [33], the different probabilities that the upper limit of the 95% CI of the risk ratio (RR) being below 1.00 (a correlate of the lower bound of the vaccine effectiveness estimate being above 0.00 [Section 9.7.3.1] demonstrating a protective effect of vaccination) was estimated and displayed in Table 1:

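### Comparators are matched geographically only on region (about 1.1 million adults each on average), so within-region differences in roll-out and incidence can confound VE

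*Protocol*

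**What the plan says.** Section 9.1.1.5 lists the matching variables as time zero of the vaccinated pair, birth year, sex, region and, if recorded, nursing-home residence. The birth-year and region part reads "it will be broad till 2-years if not enough patients to select), sex, region of the primary care practice". Section 9.3.1 repeats the rule for the 10:1 sample: comparators "will be randomly selected among those with similar birth cohort, sex and region (matched criteria").

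Region is a coarse unit here. Section 9.4 states that "BIFAP covers 7 out of 19 districts in Spain and 57% of their population overall", and section 9.5 that "BIFAP includes information of around 7.7 million patients aged" 18 or over.

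The covariates in section 9.3.4 are "lifestyle characteristics (BMI, smoking alcohol use), comorbidities, comedICATIONS, and health care utilisation prior to or at time zero", followed by a list of frailty markers. None describes practice, health area, rurality, deprivation or local incidence. The geographic subgroup in section 9.7.4.1 also stops at region and depends on sample size.

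Section 9.1.1.5 itself accepts that the way vaccine is distributed and taken up can strongly affect the size and sign of confounding. The limitations in section 9.9 do not mention differences within a region.

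**The concern.** Matching on time zero and region removes calendar trends that a whole region shares. It does not remove differences between areas of that region on the same date. If areas were called up at different speeds and also had different infection rates or access to testing, locality would be related to both exposure and outcome. Neither the matching nor the listed covariates would then break that link.

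Bias would be upward where lower-incidence areas vaccinate faster and downward where higher-incidence areas do. It could change over the campaign, and could differ between brands if supply went to different localities. The by-brand and by-month results, which the protocol plans, are therefore the most exposed. A head-to-head comparison of brands would not remove it if the brands were used in different places.

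**Working it through.** **Inputs from the Protocol.** Adults 7,720,843 (9.5); regions 7 (9.4); 14-day risk in the unexposed 0.0006057 and RR 0.331 for the one-dose vaccine (Table 1).

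**Region size.** 7,720,843 / 7 = 1,102,978 adults on average. Section 9.4 also gives 7.4 million adults, and 7,400,000 / 7 = 1,057,143. Sizes of individual regions are not given.

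**The plan's own figure.** Table 1 gives a probability of 1 that the upper 95% limit of the RR is below 1. Every row of Tables 1 and 2 reproduces as 1.000. For RR 0.331 at 1:1, each group has 3,860,421 people. Expected cases are 0.0006057 × 3,860,421 = 2,338 unexposed and 0.331 × 2,338 = 774 exposed. The standard error of log RR is about √(1/774 + 1/2,338) = 0.0415, so the 95% interval for VE is about 64.1% to 69.5%. Random error is small on these inputs, so a systematic error of a few points would matter.

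**Illustrative bias (assumptions, not document figures).** Take two equal-sized area types in one region, with coverage cA in the low-incidence and cB in the high-incidence areas, and incidence ratio r. Using a coverage snapshot for the area mix, the factor applied to the HR is

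[(cA + cB·r)/(cA + cB)] / [((1−cA) + (1−cB)·r)/((1−cA) + (1−cB))]

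and observed VE = 1 − (1 − true VE) × factor.

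| cA / cB | r | factor | true 0% reads | true 70% reads | true 95% reads |
|---|---|---|---|---|---|
| 60 / 40 | 1.5 | 0.923 | 7.7% | 72.3% | 95.4% |
| 60 / 40 | 2 | 0.875 | 12.5% | 73.8% | 95.6% |
| 60 / 40 | 3 | 0.818 | 18.2% | 75.5% | 95.9% |
| 95 / 85 | 1.5 | 0.899 | 10.1% | 73.0% | 95.5% |
| 95 / 85 | 2 | 0.841 | 15.9% | 74.8% | 95.8% |
| 95 / 85 | 3 | 0.778 | 22.2% | 76.7% | 96.1% |
| 85 / 95 | 1.5 | 1.123 | −12.3% | 66.3% | 94.4% |
| 85 / 95 | 2 | 1.222 | −22.2% | 63.3% | 93.9% |
| 85 / 95 | 3 | 1.370 | −37.0% | 58.9% | 93.1% |

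Smaller contrasts give smaller errors. With coverage of 25% and 20% and r = 1.5, the factor is 1.029 if the faster area has the higher incidence and 0.972 if it has the lower; a true 70.4% then reads 69.5% or 71.2%.

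**Against the interval.** With 60/40 and r = 2, the RR of 0.331 becomes 0.331 × 0.875 = 0.290, or VE 71.0%. That lies outside 64.1% to 69.5%. Table 1 assigns the whole adult database to one brand, so real by-brand intervals will be wider.

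**Room for finer matching.** At ages 80-84 a birth-year by sex by region cell averages 187,908 / 5 / 7 = 5,369 women and 129,936 / 5 / 7 = 3,712 men. With an assumed 50 health areas per region that is 107 and 74 people. At 85% to 95% coverage, 5% to 15% remain unvaccinated: 74 × 0.05 = 4 up to 107 × 0.15 = 16 people, against 10 comparators sought per vaccinee.

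**The case against.** The strongest reply is that the causal premise is not documented. The Protocol describes eligibility by priority group and gives no within-region figures on call-up, incidence or testing. A reader might infer that VE will be confounded, or that place of residence largely decides vaccination within a birth year; the documents support neither. This stands: the supportable claim is that the design leaves the path open.

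A reader might also infer that practice location is already in the extract because its region is a matching variable. That does not follow. Regional teams link and pseudonymise the records (9.6), investigators see anonymised data (section 10), and region may be known simply from which team supplied the data. Any fix has to depend on the code being available.

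Nor do the pool sizes make finer matching easy throughout. Whole-population cells look ample, but at high coverage the older cells fall to a handful, before removing prior infections and records below BIFAP's quality standard. People still unvaccinated in an area that has been called may be atypical, which is the behavioural selection that section 9.9 worries about. Local matching therefore exchanges some of one bias for another. This argues for stratification or tiered matching with both estimates reported; it does not justify leaving the matter out.

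The plan also has partial protections: counts of COVID-19 tests and primary care visits as covariates, stratification by month and possibly region, an open-ended covariate list, and the option of dropping comparisons where confounding is insurmountable. None of these holds area constant, and the open list commits to no area variable.

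Finally, a Cox strata term could be left to a statistical analysis plan. The matching key, however, is fixed in this protocol, and neither remedy is possible unless the code is requested.

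**Conclusion.** The point holds as a design weakness that should be addressed. Region is the only geographic matching level, no local-area covariate is listed, and the limitations do not mention the gap, although the protocol names distribution and uptake as drivers of confounding. Within-region differences can therefore confound VE, in a direction that may vary by month and brand.

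The existence, direction and size of any bias in these data cannot be established from the documents. The range of roughly 59% to 77% for a true 70% rests on two equal area types, incidence ratios of 1.5 to 3, the assumed coverage splits and a snapshot of coverage. Effects in opposite directions could partly cancel when pooled. For the two vaccines with expected VE of 95% and 94.1% the consequence is small; a true 95% reads 93.1% to 96.1% in the same scenarios. It matters more for the vaccines expected at 70.4% and 66.9%, and for comparisons between brands.

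**What to change.** 1. In section 9.1.1.1, add to the feasibility check whether a pseudonymised practice or health-area code can be supplied with the extract.
2. If it can, specify one of two approaches in sections 9.1.1.5, 9.3.1 and 9.7.3. Either keep the regional match and stratify the Cox baseline hazard by health area, or match on health area first and fall back to region when too few unvaccinated people remain. The second follows the tiered rule already used for birth year and the conditional rule for nursing homes.
3. Report the share of vaccinees matched at each level, and show the area-based estimate beside the region-only estimate.
4. If no code is available, state within-region confounding as a limitation in section 9.9.

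The cost is one extra code and a finer key or strata term. The downside is fewer comparators and some loss of precision in high-coverage age groups, where those still unvaccinated in an area may be atypical. Stratification avoids re-matching. If the time scale is time since time zero, area strata remove average differences between areas but not local waves; crossing the strata with month of time zero would address those at a further cost in precision.

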## **9.2 Setting**

This study will be conducted in Spain where the 1st COVID-19 vaccine was included in public campaigns after approval by the European Commission from 21st December 2020. The eligibility criteria will change over time according to prioritised vaccination groups as follows in Figure 1:

Due to the potentially changing incidence of COVID-19 over time and prioritised vaccination groups, comparisons within the study periods and prioritised criteria will be established as much as possible.

According to the 1st prioritized groups (see Figure above), the **study period** will begin on the 21st of December 2020. The end of study period will be the last date of data received at the start of the data collection. Since the vaccines start to request the vaccination for young people (for example: Pfizer requested to the FDA to expand use of its Covid-19 vaccine to adolescents ages 12 to 15 on 9th April 2021), no age restriction will be applied for the source population.

No sex restriction will be applied.

In BIFAP, as per quality and quantity criteria for research, and in order to ensure precise anamnesis, only those clinical histories considered up-to-standard are included in pharmacoepidemiological studies.

## 9.3 Variables

The measurement of exposure status, eligibility criteria, outcomes, and covariates defined below will be defined in the data source(s) and subsequently used in analysis.

### 9.3.1 Exposure Assessment and Time At Risk

Data will be collected from BIFAP database with data from Spain (described in [Data Sources](#)).

**Inclusion criteria** to the Source population: up-to-standard,  $\geq 1$  year baseline information in January 2021 in BIFAP. The last date of filling all the inclusion criteria will be the inclusion date. No restriction to age or sex will be applied.

**Exclusion criteria:** Patients with prevalent COVID vaccinations or infections ever before (i.e. washout period) the inclusion criteria will be excluded.

**Stop date:** the last moment of the following criteria will define the stop date to contribution: covid-19 infection, death, loss to follow-up and end of study period (the last date available in the data source at data collection).

**Exposure assessment:** The 1st vaccination recorded after the inclusion date will be the time zero for patients included in the vaccinated group, as explained in section 'Definition of Time Zero' [9.1.1.4](#).

From the source population, 10 individuals unvaccinated on or before time zero of the vaccinated pair (10:1) will be randomly selected among those with similar birth cohort, sex and region (matched criteria). Patients included in the comparison group, may be vaccinated later during their follow-up period and then contribute to the vaccinated group (from the date of vaccine administration ahead; i.e. time zero for the vaccinated group).

\*Note: All individuals vaccinated during their follow-up contribution will be included in the vaccinated group. While, a random selection of the unvaccinated individuals will be included as unvaccinated group.

The date and type of vaccine administered will be collected from the **Table of Vaccine** from BIFAP data model. In particular, Covid-19 vaccinations will be ascertained from official covid-19 vaccination registries and provided by the regional governments. The coding system is not known yet. The feasibility analysis will include an evaluation of the coding type, whether or not vaccines are recorded according to standardised system or not. We expect that either ATC07 (J07????) or National Code (CNF [Código Nacional de

Farmacia]) specific for pharmaceuticals in Spain is available for all vaccines administered.

For the vaccines currently available, those with a 2-dose regimen, the second dose must be administered 21/28 days after the 1st dose. In order to identify potential data **entry errors** (e.g., two vaccination records too closed or 3 doses recorded, may indicate double recording of the same vaccination) and cut-off points, a description of interval between doses will be performed beforehand.

Current vaccines are intended to give protection at least for 21 and 28 days after the 2nd dose, however the protection in the median-long run is unknown. Thus, in order to estimate the duration of the effectiveness, the follow-up period after 2nd dose will be divided as aforementioned.

The **follow-up** period will be the time between time zero and stop date.

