#### **9.1.1.4 Definition of Time Zero**

In studies of vaccinated versus unvaccinated persons, researchers must determine the appropriate time point at which to identify patients and begin follow-up. Aligning the evaluation of eligibility criteria, covariate assessment, exposure assignment, and beginning of follow-up (time zero) avoids selection bias and immortal person-time bias and addresses a well-defined study question [13].

Time zero is the time when the vaccination status is assigned; all eligibility criteria must be fulfilled at that point, and COVID outcomes must start to be counted at that point [14].

Time zero in the vaccinated group will be the date when the 1st dose of COVID-19 vaccine is administered (i.e. recorded). That date will be also used for the unvaccinated pairs as Time zero.

The aim of the **Main analysis** will be the estimation of the effectiveness  $\geq 15$  days after full vaccination series whether 1- or 2-doses regimens (and regardless of delayed completion of 2-dose vaccine series ,i.e. recorded dates will be accepted as real world data even though the time between doses are not fully adjusted to recommended intervals). Analysis will be performed by vaccine brand.

In order to properly observe the moment when the effect of the vaccination starts, the period between 1st Dose and 14 days after the 2nd dose will be divided and compared with unvaccinated patients. Thus, at least 5 cut-of periods will be identified along each patient's follow-up contribution:

- 1) Non-exposed period among Unvaccinated patients (Reference for Effectiveness estimation)

- 2) D1-induction time: up-to 14 days after 1st dose
- 3) D1-effectiveness: 15 days after 1st dose to 2nd dose
- 4) D2-induction time: up-to 14 days after 2nd dose
- 5) D2-effectiveness in the short run: 15-90 days after 2nd dose
- 6) D2-effectiveness in the medium run: 91-180 days after 2nd dose
- 7) D2-effectiveness in the long run:  $\geq 181$  days after 2nd dose

[figure not shown]

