The last date available in the data source at data collection will be the end of the Study time period.

\*The study population is defined in terms of Exposure (instead of Disease/Indication)

‡Duration of follow-up: Inclusion date and stop date to follow-up define the Duration of follow-up.

Section 5: Exposure definition and measurement	Yes	No	N/A	Section Number
5.1 Does the protocol describe how the study exposure is defined and measured? (e.g. operational details for defining and categorising exposure, measurement of dose and duration of drug exposure)				9.3.1
5.2 Does the protocol address the validity of the exposure measurement? (e.g. precision, accuracy, use of validation sub-study)				9.1.1.3
5.3 Is exposure categorised according to time windows?				9.1.1.4
5.4 Is intensity of exposure addressed? (e.g. dose, duration)				9.1.1.4
5.5 Is exposure categorised based on biological mechanism of action and taking into account the pharmacokinetics and pharmacodynamics of the drug?				9.1.1.4
5.6 Is (are) (an) appropriate comparator(s) identified?				9.3.1;9.1.1.4*

Comments:

\*We have discarded to select other control groups due to the reason explained in 9.1.

Section 6: Outcome definition and measurement	Yes	No	N/A	Section Number
6.1 Does the protocol specify the primary and secondary (if applicable) outcome(s) to be investigated?				8; 9.3.3
6.2 Does the protocol describe how the outcomes are defined and measured?				8; 9.3.3
6.3 Does the protocol address the validity of outcome measurement? (e.g. precision, accuracy, sensitivity, specificity, positive predictive value, use of validation sub-study)				8; 9.1.1.2

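### Section 9.3.1 ties the prior-infection exclusion to the inclusion date, while 9.1.1.4 requires eligibility at time zero; as worded, someone infected between the two dates can still be selected in either arm

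*Protocol*

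**What the plan says.** The relevant rules are in three places in the protocol.

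- **Exclusion (9.3.1).** "Patients with prevalent COVID vaccinations or infections ever before (i.e. washout period) the inclusion criteria will be excluded". The look-back therefore ends when the inclusion criteria are met. The inclusion criterion is at least one "year baseline information in January 2021 in BIFAP", and "The last date of filling all the inclusion criteria will be the inclusion date".
- **Time zero, vaccinated (9.3.1).** The first "vaccination recorded after the inclusion date will be the time zero for patients included in the vaccinated group".
- **Comparators (9.3.1).** "10 individuals unvaccinated on or before time zero of the vaccinated pair (10:1) will be randomly selected among those with similar birth cohort". Region and sex are the other matching factors there. The matching list in 9.1.1.5 adds nursing-home residence if available, but not infection history. Section 9.3.2 adds no further eligibility criteria.
- **Principle (9.1.1.4).** Of time zero: "all eligibility criteria must be fulfilled at that point".
- **Follow-up.** In 9.3.1 the follow-up "period will be the time between time zero and stop date". In Annex 1 (ENCePP checklist, comments to Section 4): "Inclusion date and stop date to follow-up define the Duration of follow-up".
- **Stop date (9.3.1).** Infection, death, loss to follow-up and end of study are listed, and the latest of these is named as the stop date.

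**The concern.** The primary outcome is incident laboratory-confirmed infection, dated by the first sample (9.3.3.1). A person with a positive sample before time zero is no longer at risk of a first infection and may be partly protected against a second. The exclusion should keep such people out, but its date is set at inclusion and not at the point where arms are assigned and counting begins.

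If infection alters whether or when someone is vaccinated, the share of previously infected people can differ between the arms, and the hazard ratio then moves. There is also a practical risk: a programmer following 9.3.1 to the letter and one following the principle in 9.1.1.4 would build different primary cohorts.

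**Working it through.** **1. Does the time-zero principle cure the wording?** Take a person with a long record, included in January 2021, infected in February, and a candidate comparator in April or a vaccinee in June. At time zero the test in 9.3.1 is whether an infection preceded inclusion. It did not, so the criterion is fulfilled at time zero and the principle in 9.1.1.4 is formally satisfied. The principle shows the intention, but the criterion does not carry it out.

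**2. Does the stop rule remove this person?** It depends on the reading.

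| Stop rule | Follow-up starts | Result for the February infection |
|---|---|---|
| Earliest event | Inclusion (Annex 1) | Contribution ended in February; no later person-time |
| Earliest event | Time zero (9.3.1) | Stop precedes entry; negative duration, no person-time in a Cox model |
| Latest event (as written) | Either | Infection does not end contribution; person-time continues |

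The first two rows are harmless for person-time. Only the third is the literal text. The rule that vaccinees are those vaccinated during their follow-up contribution helps only if infection ends contribution, and it does not govern the draw of comparators.

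**3. Is there a named adjustment?** Prior infection is not in the comorbidity list of 9.3.4. The health care utilisation list there has the total number of COVID-19 tests, not their results.

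**4. The plan's own figure.** Table 1 gives a probability of 1 that the upper 95% limit of the RR is below 1.00. Inputs from 9.5: N = 7,720,843, risk in the unexposed 0.0006057, RR 0.331 (the weakest effect in the table), ratio 1:1.

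- Expected unexposed cases: 3,860,421 × 0.0006057 ≈ 2,338; exposed: 2,338 × 0.331 ≈ 774.
- SE of log RR ≈ √(1/774 + 1/2,338) ≈ 0.0415.
- −ln(0.331)/0.0415 − 1.96 ≈ 24.7, so the probability is 1.000.

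The figure is reproduced. Removing under 1% of people leaves it at 1.000, so the fix does not affect precision.

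**5. How many people?** The rate is 60.57 per 100,000 per 14 days (9.5, symptomatic cases), assumed constant from 1 January.

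- To 22 March, 80 days: 0.0006057 × 80/14 = 0.35%, about 26,700 of 7,720,843.
- To 30 June, 180 days: 0.0006057 × 180/14 = 0.78%, about 60,100.
- Compounding over 26 weeks: 1 − (1 − 0.0006057)^13 = 0.79%.

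**6. Effect on VE.** Suppose these people stay in person-time and are fully protected. With shares f_v (vaccinated) and f_u (unvaccinated), HR_obs = HR × (1 − f_v)/(1 − f_u).

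- Equal shares: HR_obs = HR, no bias.
- 0.78% in the unvaccinated only: 0.331/0.9922 = 0.3336, VE 66.6%.
- 0.78% in the vaccinated only: 0.331 × 0.9922 = 0.3284, VE 67.2%.
- True HR of 1.00 in the dose-1 induction window: 1/0.9922 = 1.008, or 0.992.

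Larger shares are pure assumptions. With f_u = 2%, f_v = 0, 66.9% becomes 66.2%; with f_u = 5%, f_v = 1%, 65.5%; with f_u = 0.5%, f_v = 2%, 67.4%. For comparison, five times the protocol's rate would give 3.9% after 26 weeks.

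**The case against.** The strongest reply is that the protocol already states the right principle. Section 9.1.1.4 asks for every eligibility criterion to hold at time zero, and 9.3.1 refers to that section when it defines time zero. Infection is a listed stop criterion, and only people vaccinated during their contribution count as vaccinees. Read sensibly, a February infection has ended contribution before a June vaccination. Comparators share the pair's calendar date, birth year, sex and region, which limits imbalance.

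Much of this stands. The intention is clear, and under an earliest-event stop rule the affected people add no person-time whichever follow-up start is used. What does not stand is that the text already secures this: the exclusion looks back from the wrong date, and the stop rule as written takes the latest event.

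A reader might infer more: that previously infected people certainly enter both arms, or that VE is materially biased in a known direction. The documents do not support either. They give no infection shares by arm, and equal shares produce no bias. A scenario with 5% of one arm affected is about 6 to 14 times the 0.78% to 0.35% that the protocol's own rate implies. Nor is that range a firm lower bound: counting symptomatic cases only pushes it down, but it also stretches one 14-day value over six months.

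**Conclusion.** The point holds as an internal inconsistency in the definition of the primary cohort. Section 9.3.1 anchors the exclusion at inclusion, 9.1.1.4 expects eligibility at time zero, and the stop rule and the two follow-up starts do not reliably close the gap. The literal text lets a person infected in between be selected in either arm.

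The likely size is small. About 0.35% to 0.8% of the source population is affected over 80 to 180 days, given a constant symptomatic-only rate. Even with total imbalance and full protection at 0.78%, a VE of 66.9% shifts by about 0.3 points, in a direction the documents do not determine. The case for acting is that the cohort definition is ambiguous and cheap to repair, not that a large bias has been shown.

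**What to change.** Make three wording changes before extraction.

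1. In 9.3.1, restate the exclusion as no recorded COVID-19 infection and no COVID-19 vaccination before time zero, checked for each vaccinee on their own time zero and for each candidate comparator on the pair's time-zero date.
2. In 9.3.1, define the stop date as the earliest of the listed events.
3. In Annex 1, amend the checklist comment so that follow-up starts at time zero, as in 9.3.1.

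The cost is a date filter on data already being linked and slightly fewer eligible people; Table 1's probability stays at 1. Counting infections recorded only as a diagnosis code could be a sensitivity analysis. It is not part of the required change, because 9.7.4.2 says the validity of that coding is unknown.
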